1.2.2. Summary of Clinical Data with Lumasiran

Lumasiran is being investigated in 2 ongoing clinical studies, Study ALN-GO1-001 and Study ALN-GO1-002.

Study ALN-GO1-001 is a 2-part (single-ascending dose [SAD] and multiple-ascending dose [MAD]) study designed to evaluate the safety, tolerability, PK, and PD of lumasiran in healthy adult subjects and in adult and pediatric patients with PH1. In the SAD part of the study (Part A), healthy adult subjects were randomized to receive one single blind dose of lumasiran (0.3-6.0 mg/kg) or placebo (6:2). In the MAD part of the study (Part B), patients \geq 6 years of age with PH1 and eGFR > 45 mL/min/1.73 m² were randomized 3:1 to receive single blind doses of lumasiran or placebo at 1 mg/kg monthly for 3 doses, 3 mg/kg monthly for 3 doses or 3 mg/kg every 3 months for 2 doses. Patients who initially received placebo transitioned to an open-label portion of the study to receive doses of lumasiran. The primary objective is to evaluate the safety and tolerability of subcutaneously administered lumasiran. Secondary and exploratory objectives of the study include the characterization of plasma and urine PK and the evaluation of the PD effect, including glycolate and oxalate levels.

Study ALN-GO1-002 is a Phase 2 open-label extension study to evaluate the long-term safety, PK, and PD of lumasiran in patients with PH1 who have completed Study ALN-GO1-001.

Available safety data indicate that lumasiran has an acceptable safety and tolerability profile across all dosing regimens evaluated. Preliminary data from Study ALN-GO1-001 demonstrate a mean maximal reduction in 24-hour urinary oxalate of 64% (Cohorts 1-3) and achievement of normal to near-normal levels of urinary oxalate (<0.70 mmol/24h/1.73 m²) in patients dosed with lumasiran (range: 0.29 to 0.67 mmol/24h/1.73 m²). Further information on the chemistry, pharmacology, efficacy, and safety of lumasiran is provided in the current edition of the Investigator's Brochure.

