7.2.5.2. Secondary Endpoints

To control the overall type I error, these secondary endpoints will be tested in the following hierarchical order:

- Absolute change in 24-hour urinary oxalate corrected for BSA from baseline to Month 6
- Change in 24-hour urinary oxalate:creatinine ratio (value/ULN) from baseline to Month 6
- Proportion of patients with 24-hour urinary oxalate level at or below 1.5 x ULN at Month 6
- Proportion of patients with 24-hour urinary oxalate level at or below ULN at Month 6
- Percent change in plasma oxalate from baseline to Month 6
- Absolute change in plasma oxalate from baseline to Month 6

Continuous endpoints will be analyzed using an MMRM approach similar to the one described for the primary endpoint. Binary endpoints will be analyzed using the Cochran-Mantel-Haenszel test stratified by baseline urinary oxalate. The odds ratio and the differences in proportions with corresponding 95% confidence will also be summarized.

Secondary endpoints assessed beyond Month 6 will be summarized descriptively. Change in eGFR over time will also be summarized descriptively.

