### 3.2.2. Secondary Endpoints

- Absolute change in 24-hour urinary oxalate corrected for body surface area (BSA) from baseline to Month 6
- Percent change in 24-hour urinary oxalate: creatinine ratio from baseline to Month 6
- Percent change in plasma oxalate from baseline to Month 6
- Proportion of patients with 24-hour urinary oxalate level at or below 1.5xULN at Month 6
- Proportion of patients with 24-hour urinary oxalate level at or below ULN at Month 6
- Absolute change in plasma oxalate from baseline to Month 6
- Change in in estimated glomerular filtration rate (eGFR) from baseline to Month 6
- Change from baseline (percent and absolute) 24-hour urinary oxalate excretion, percentage of time that 24-hour urinary oxalate is ≤1.5 × ULN, 24-hour urinary oxalate: creatinine ratios and eGFR in the extension periods

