### 4. PATIENT POPULATION

### 4.1. Patient Definitions

The populations (analysis sets) are defined as follows:

- Full Analysis Set (FAS): All randomized patients who received any amount of study drug. Patients will be analyzed according to the treatment to which they were randomized.
- Safety Analysis Set: All patients who received any amount of study drug. Patients will be analyzed according to the treatment actually received.
- PK Analysis Set: All patients who received any amount of study drug and have at least 1 PK concentration measurement.
- All Lumasiran Treated Set: All patients who received any amount of lumasiran, including patients who took lumasiran during the 6-month double-blind period and patients who initially took placebo during the 6-month double-blind period and then switched to lumasiran during the extension period.
- Plasma Oxalate Analysis Set: All patients who received any amount of study drug and have a baseline plasma oxalate level ≥ 1.5\*LLOQ

The primary population used to evaluate efficacy will be the Full Analysis Set (FAS) for the primary and secondary endpoints during the 6-month double-blind period. Safety during the double-blind period will be analyzed using the Safety Analysis Set. The PK Set will be used to evaluate the PK endpoints. The All Lumasiran Treated Set will be used to summarize the long-term efficacy and safety of lumasiran. The Plasma Oxalate Analysis Set will be used to evaluate the endpoints for the change from baseline in plasma oxalate.

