For continuous endpoints (including eGFR), descriptive statistics will be generated by treatment arm. LS Mean (+/- standard error) by treatment arm will be plotted for continuous PD endpoints. Spaghetti plots will also be generated for all continuous endpoints.

Table 2: Analysis of Secondary Endpoints to Month 6^

Endpoints	Statistical Method	Analysis Population
Absolute change in 24-hour urinary oxalate to Month 6	MMRM	Full Analysis Set
Percent change in 24-hour urinary oxalate:creatinine ratio to Month 6	MMRM	Full Analysis Set
Percent change in plasma oxalate from baseline to Month 6	MMRM	Plasma Oxalate Analysis Set
Proportion of Patients with 24-hour urinary oxalate ≤1.5xULN at Month 6	СМН	Full Analysis Set
Proportion of Patients with 24-hour urinary oxalate ≤ULN at Month 6	СМН	Full Analysis Set
Absolute change in plasma oxalate from baseline to Month 6	MMRM	Plasma Oxalate Analysis Set

^eGFR will be summarized descriptively (i.e. no formal testing) because this endpoint is not expected to change during the 6 months.

The following secondary endpoints which are assessed beyond Month 6 will be summarized to demonstrate long-term durability of lumasiran using the All Lumasiran Treated Set.

Descriptive statistics of percent change in 24-hour urinary oxalate at and after 6 months of lumasiran will be presented by treatment sequence (lumasiran/lumasiran, placebo/lumasiran) and the all treated arm (pooling treatment arms). A Wilcoxon-signed rank test (2-sided) will be conducted to test the null hypothesis of no change from baseline at selected timepoints (Months 6, 12, 18, 30, 36, 42 and 54). Additionally, the mean percent change from baseline with associated 95% (CIs) confidence intervals at each selected timepoint will also be presented. Supportive figures of mean (+/-standard error) percent change will be generated.

Descriptive statistics of percent change in 24-hour urinary oxalate will also be generated at visits during the entire study using the FAS set. Supportive figure of mean (+/- standard error) percent change will also be generated. An analysis of the percentage of time that 24-hour urinary oxalate level is at or below the near-normalization threshold will be summarized. A patient is considered to have met the threshold if the 24-hour urinary oxalate level is  $\leq 1.5 \text{xULN}$  at a post-baseline visit.

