For each patient, the percentage of time that 24-hour urinary oxalate level is at or below the near normalization threshold (ie,  $\leq 1.5 \text{xULN}$ ) will be calculated as follows:

$$\frac{cumulative\ months\ at\ or\ below\ near\ normalization\ threshold}{cumulative\ months\ of\ valid\ assessments}\times 100$$

where cumulative months at or below the near normalization will be defined as the summation across all intervals that met the threshold and cumulative months of valid assessments will be defined as the summation across all valid post-baseline collections.

Given that the sample collection varies during the study (e.g. monthly up until M9, every 3 months until M24, every 6 months until Month 60), the calculation will take into account the following considerations:

- Time will be restricted to a maximum of 36 months on lumasiran (that is, up to protocol defined month 36 visit for lumasiran/lumasiran arm or up to protocol defined month 42 visit for placebo/lumasiran arm) or premature treatment discontinuation, whichever occurs first.
- A linear interpolation method will be used for to determine the bookend dates at which the patient crossed into the threshold and crossed out of the threshold.

Descriptive statistics of percentage of time at or below the threshold (among the subset of patients who had at least one post-baseline value which met threshold) will be presented for each treatment sequence arm and the all treated arm. In addition, the number of patients and associated percentage of patients in each category (e.g. <25%,  $\ge25\%$  to <50%,  $\ge50\%$  to <75%,  $\ge75\%$  to 100%) will also be presented.

Descriptive statistics of eGFR at and after 6 months of lumasiran will be presented. Shift tables of eGFR categories from baseline to post-baseline visits and an overall worst post-baseline will also be generated.

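### The mean percentage of time at or below 1.5 × ULN omits patients who never reached the threshold, so it overstates time near normal whenever there are such patients

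*SAP*

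**What the plan says.** SAP 3.2.2 lists among the secondary endpoints for the extension periods the "percentage of time that 24-hour urinary oxalate is ≤1.5 × ULN", with no condition on who is counted. Section 2 of the protocol lists the same endpoint, also without a condition.

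SAP 7.2 says that the secondary endpoints beyond Month 6 "will be summarized to demonstrate long-term durability of lumasiran using the All Lumasiran Treated Set". SAP 4.1 agrees ("The All Lumasiran Treated Set will be used to summarize the long-term efficacy and safety of lumasiran") and defines that set by exposure alone: "All Lumasiran Treated Set: All patients who received any amount of lumasiran".

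SAP 7.2 then defines a per-patient percentage. The numerator is the cumulative months at or below the threshold, and the denominator is the cumulative months covered by valid post-baseline collections. Time is capped at 36 months on lumasiran or at premature discontinuation. The descriptive statistics of this percentage, by treatment sequence and for all treated patients, are to be presented "among the subset of patients who had at least one post-baseline value which met threshold". The following sentence adds "the number of patients and associated percentage of patients in each category", with example classes of below 25%, 25% to below 50%, 50% to below 75%, and 75% to 100%. It neither repeats the restriction nor names a denominator.

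The protocol (7.2.5.2) says only: "Secondary endpoints assessed beyond Month 6 will be summarized descriptively".

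**The concern.** Whether a patient ever meets the threshold is part of the outcome being summarised. Restricting the summary to patients who did so drops exactly those with the lowest possible value. The mean and median then answer a narrower question (how long levels stay near normal in patients who get there) than the endpoint asks (how much of their time treated patients spend near normal). The pooled column would be labelled as all treated patients while leaving some of them out.

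The SAP's other restricted population shows the contrast. The Plasma Oxalate Analysis Set is defined by a baseline value, has a name, and is explained in sections 4.1, 7.2 and 8. The restriction here depends on post-baseline results, has no named set and is given no reason.

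At stake is the accuracy of one secondary endpoint that the SAP uses to show durability. No hypothesis test depends on it.

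**Working it through.** The documents give no expected value for this endpoint, so there is no planned figure to reproduce. The check has three steps.

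**1. Value for a patient who never meets the threshold.** By the SAP 7.2 formula the numerator is 0 and, with at least one valid post-baseline collection, the denominator is positive, so the percentage is 0%. A patient with no valid post-baseline collection has no defined percentage, drops out of either version and causes no bias.

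**2. Size of the bias.** Let N be the number of evaluable patients, k the number who never meet the threshold, and m the mean among the rest.

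- All-patient mean = m × (N − k)/N
- Overstatement = m × k/N percentage points
- Reported mean ÷ all-patient mean = N/(N − k), which exceeds 1 for every k ≥ 1 and equals 1 only at k = 0

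Inputs: N = 30 is the planned enrolment (protocol 7.1). The sequences have about 20 and 10 patients under 2:1 randomisation. All are taken to have a valid post-baseline collection on lumasiran. Both m and k are assumed: m = 80%, with a range of 60% to 90%.

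| N | k | All-patient mean if the reported mean is 80% | Overstatement for m = 60% to 90% |
|---|---|---|---|
| 30 | 0 | 80.0% | 0 |
| 30 | 1 | 80 × 29/30 = 77.3% | 2.0 to 3.0 points |
| 30 | 3 | 80 × 27/30 = 72.0% | 6.0 to 9.0 points |
| 30 | 6 | 80 × 24/30 = 64.0% | 12.0 to 18.0 points |
| 20 | 1 | 80 × 19/20 = 76.0% | 3.0 to 4.5 points |
| 10 | 1 | 80 × 9/10 = 72.0% | 6.0 to 9.0 points |

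**3. Could k be above zero?** SAP Appendix A gives a ULN of 0.514 mmol/24h/1.73m², so the threshold is 1.5 × 0.514 = 0.771. Randomisation is stratified at a baseline of 1.70.

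- With the 54% mean reduction assumed in the sample-size section, a baseline of 1.70 falls to 1.70 × 0.46 = 0.782, just above the threshold.
- The reduction needed is 1 − 0.771/1.70 = 54.6% from 1.70, 61.5% from 2.0 and 69.2% from 2.5.
- One qualifying value is enough, so a patient's best value matters more than the average. Protocol 1.2.2 gives a mean maximal reduction of 64% in Phase 1. On that figure 1.70 falls to 1.70 × 0.36 = 0.612, which qualifies. A baseline above 0.771/0.36 = 2.14 would not.
- The same section reports levels "in patients dosed with lumasiran (range: 0.29 to 0.67" mmol/24h/1.73m²), all below 0.771. The Phase 1 patients had eGFR above 45, against 30 or more here, and the assay may differ.

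So k may well be zero or small, but the plan's own figures do not rule out patients with a high baseline who never qualify.

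**The case against.** The strongest reply is that the summary is descriptive, outside the testing hierarchy, and openly conditional. How long near-normal levels last in patients who reach them is a coherent durability question, and as an answer to that question the figure is not wrong. This stands as far as it goes. It supports keeping the conditional summary, but not making it the only planned mean and median for an endpoint that is listed without the condition.

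Second, exclusion requires missing the threshold at every collection. The schedules give about 16 collection visits through Month 36 for lumasiran/lumasiran and about 11 from Month 7 to Month 42 for placebo/lumasiran. That is a fair reason to expect a small k, and nothing in the documents points to k = 6; that row is an outer illustration. It applies less to a patient who discontinues early, who has fewer chances to qualify.

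Third, the omission is partly visible. SAP 5.2 requires n, the size of the set is tabulated, and per-patient listings and individual plots are planned. A reader could approximately recover the all-patient mean, but not the median or quartiles. The category table may include patients who never met the threshold under the below-25% class. Its classes are only examples, but its denominator is unstated and no 0% class is shown.

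Fourth, SAP section 8 records changes from SAP version 1.0, so its silence on the restriction proves little. This is accepted; the case rests on sections 3.2.2, 4.1 and 7.2.

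Finally, entry is allowed from 0.70, below 0.771, and the SAP does not say where interpolation starts. If it started at baseline, a patient with no qualifying post-baseline value could score slightly above 0%. The denominator wording points to post-baseline data only, and the direction of the bias would change only in contrived cases.

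**Conclusion.** The concern holds. As written, the only planned mean and median for this secondary endpoint are conditional on the outcome and do not match the endpoint as listed or the All Lumasiran Treated Set. Relative to that target, the mean is inflated by N/(N − k) whenever at least one patient with valid post-baseline collections never meets the threshold. There is no bias at k = 0.

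The size cannot be fixed from the documents, because neither k nor the mean is given. For one such patient and a reported mean of 60% to 90%, the overstatement is 2 to 3 points in 30 patients and 6 to 9 points in a sequence of 10. The primary analysis, the hierarchy and the type I error are untouched.

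**What to change.** In SAP 7.2, remove the restriction and summarise all patients in the All Lumasiran Treated Set with at least one valid post-baseline 24-hour collection, entering 0% for those who never met the threshold. Use and state the same denominator for the category table, and add a 0% class. Keep the present summary as supportive output, labelled as conditional on having met the threshold at least once and showing the number excluded.

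This changes one phrase and one table row and needs no new data. The reported mean may be somewhat less favourable. If every evaluable patient meets the threshold at least once, the result is the same and the table shows that nobody was left out.

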# 7.3. Subgroup Analysis

Subgroup analyses will be conducted to assess the consistency of the treatment effect during the double-blind period for the primary endpoint within the following subgroups:

- Age (6-11, 12 to 17 vs. ≥18 years at screening)
- Gender (Male vs. Female)
- Race (White vs. Non-White)
- Baseline 24-hour urinary oxalate corrected for BSA (≤1.70 mmol/24h/1.73m^2 vs. (>1.70 mmol/24h/1.73m^2)

- Baseline eGFR ( $\leq 60 \text{ vs.} > 60$ )
- History of renal stones (Yes vs. No)
- Baseline vitamin B6 use (Yes vs. No)
- Region 1 (North America [including US and Canada] vs. Other (outside of North America)).
- Region 2 (Europe vs. Other (outside of Europe))

Other subgroups may be examined, if deemed appropriate.

Subgroup analyses will be performed for the primary endpoint of percent change in 24-hour urinary oxalate corrected for BSA to Month 6 using the FAS population. A forest plot will be generated to illustrate the estimated treatment effect along with the associated 95% confidence interval. If the number of patients in a subgroup for either arm is less than 5 patients, then only descriptive statistics will be generated.

The subgroup analyses may be performed for secondary endpoints.

### 7.4. Exploratory Analysis

Exploratory endpoints will compare lumasiran versus placebo during the DB period using the Full Analysis Set. These endpoints will also be summarized during the long-term efficacy of lumasiran by treatment sequence arms (lumasiran/lumasiran, placebo/lumasiran) and all treated arm (pooling treatment sequence arms) using the All Lumasiran Treated Set.

For changes in PD parameters (urinary oxalate: creatinine ratios as assessed in random spots, plasma glycolate, 24-hour urinary glycolate: creatinine ratio, and urinary glycolate: creatinine ratios as assessed in random spots), descriptive statistics will be presented by visit.

To understand the treatment effect of lumasiran on kidney function, changes over time in renal stone events (as per section 6.3.3. in the protocol) and nephrocalcinosis will be explored.

To evaluate changes in renal stones, protocol defined events will be collected continuously during the study (i.e. renal stone event defined as at least one of the following: visit to heath care provider because of a renal stone, medication for renal colic, stone passage and macroscopic hematuria due to a renal stone). The total number of patients with a renal stone event, total number of renal stone events, total person-days at risk and rate of renal stone events during the respective period (i.e. DB period or during lumasiran treatment) will be presented. The rate will be calculated as total number of renal stone events divided by total person-days at risk during the respective period.

To evaluate changes in nephrocalcinosis, a renal ultrasound will be performed at baseline and at Months 6, 12, 24, 36 48 and 60. The renal ultrasound will also measure the number of kidney stones, the size of the kidney stones, report the location of kidney stones and grade the nephrocalcinosis (range: 0 to 3) where a higher grade indicates greater severity. Changes in the grade of nephrocalcinosis for each kidney (right or left) will be categorized into 3 groups ('no change', 'improving', and 'worsening'). At each post-baseline visit, the number and associated percentage of patients in the following 4 categories of the overall change (i.e., accounting for

both kidneys), 'no change', 'improving', 'worsening', and 'indeterminate (one kidney improving and one worsening', will be presented. Descriptive statistics will also be generated.

To explore changes in Quality of Life (QoL), patient resource use and patient experience (or caregiver experience) questionnaires will be collected at baseline and every 6 months during the course of the study.

Changes in patient resource use and/or patient experience (or caregiver experience) will be summarized descriptively.

The QoL instrument will be based upon the age of the patient at screening and the instrument will be used consistently throughout the study. Table 3 outlines the QOL instruments to be collected based upon age at screening.

**Table 3:** QOL instruments by Age at Screening (<18 years old vs. ≥ 18 years old)

Age at Screening	QOL Instruments	Domains/Subscales	Notes	
≥18 years old	EQ-5D-5L	5 domains (5 ordinal levels per domain): mobility, self-care, usual activities, pain/discomfort and anxiety/depression  1 scale: Visual Analogue Scale Score  1 summary score: Index Score (representing health state utility for an average individual with the same combination of per-domain responses as the trial participant in question)	VAS is a common variable in both instruments	
<18 years old	EQ-5D-Y	5 domains (3 ordinal levels): mobility, looking after myself, doing usual activities, pain/discomfort and feeling worried/sad/unhappy 1 scale: Visual Analogue Scale Score		
≥18 years old	KDQOL-36	5 subscales: SF-12 Physical Component Summary Score, SF-12 Mental Component Summary Score, Symptoms/Problems, Effects of Kidney Disease and Burden of Kidney Disease	No common variables	
<18 years old	PedsQL	4 domains: Physical Functioning, Emotional Functioning, Social Functioning and School Functioning 3 summary scores (total score, physical health summary score and psychosocial health summary score)	- variables	
<18 years old	PedsQL ESRD	7 domains: General Fatigue, About My Kidney Disease, Treatment Problems, Family and Peer Interaction, Worry, Perceived Physical Appearance, and Communication 1 summary score: Total Score		

As shown in Table 3, the EQ-5D will be collected to measure general health status in both pediatrics and adult patients with PH1. The VAS and Index Score will range from 0 to 100 where lower values represent a worse quality of life.

During the double-blind period, the change from baseline to month 6 in VAS (pooling: EQ-5D-5L and EQ-5D-Y) will be summarized by randomized treatment arm (lumasiran or placebo),

For the EQ-5D instrument, categorical summaries of the percentage of patients reporting ordinal responses for each of the 5 domains will be presented. Descriptive statistics of actual and change in VAS and Index score (applies to only EQ-5D-5L) will also be generated.

In addition, KDQOL-36 will be collected for adult patients to assess kidney disease specific measures and PedsQL will be collected for pediatric patients to further assess quality of life. In both instruments, values range from 0 to 100 and lower scores indicate a worse self-reported QoL. Descriptive statistics will be generated for each instrument.

